4.4.3.3 SymptoMScreen

The SymptoMScreen is formed of 12 distinct domains which list common MS symptoms including mobility, dexterity, vision, fatigue, cognition, bladder function, sensation, dizziness, spasticity, body pain, depression and anxiety. Extent of limitations affected by symptoms is scored on a 7-point likert scale. Item scores are summed to form a total score and a higher score corresponds to worse symptom limitations.

	Items #	Item Scores
SymptoMScreen score	1-12	0 = Not affect at all 1 = Very mild limitation / I make minor adjustments 2 = Mild limitation/ I make frequent adjustments 3 = Moderate limitation/ I reduced my daily activities 4 = Severe limitation/ I gave up some activities 5 = Very severe limitation/ I'm unable to do many daily activities 6 = Total limitation/ I'm unable to do most daily activities

A total score will be calculated

	Calculation for total score	Range
SymptoMScreen score	The 12 items are summed for patients with all 12 questions non missing	0-72

The SymptoMScreen total score will be summarized descriptively by visit. No imputation of missing data will be performed. The mean change of SymptoMScreen total score from baseline to weeks 24, 48 and 96 will be summarized descriptively.

Proportion of patients with at least one symptom causing moderate limitation (≥ 4) and above will be calculated at baseline and at follow up weeks 24, 46 and 96.

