# SYMPTOM SCREEN

Please circle **one number** that best describes how MS has affected each function. For example, if it takes you longer to type or text, you might rate your hand function as 'mildly limited' (circle '2'), but if you gave up typing completely, you might rate your hand function as 'very limited' (circle '4').

	0 – not affected at all	1 – very mild limitation/ I make minor adjustments	2 – mild limitation/ I make frequent adjustments	3 – moderate limitation/ I reduced my daily activities	4 – severe limitation/ I gave up some activities	5- very severe limitation/ I'm unable to do many daily activities	6 – total limitation/ I'm unable to do most daily activities
Walking	0	1	2	3	4	5	6
Hand function/Dexterity Poor hand coordination, tremors	0	1	2	3	4	5	6
Spasticity & Stiffness Muscle cramping or muscle tightness	0	1	2	3	4	5	6
Bodily Pain Aches, tenderness	0	1	2	3	4	5	6
Sensory symptoms Numbness, tingling, or burning	0	1	2	3	4	5	6
Bladder control Urinary urgency, frequency	0	1	2	3	4	5	6
Fatigue	0	1	2	3	4	5	6
Vision Blurry vision, double vision	0	1	2	3	4	5	6
Dizziness Feeling off balance, 'spinning'/vertigo	0	1	2	3	4	5	6
Cognitive function Memory, concentration problems	0	1	2	3	4	5	6
Depression Depressed thoughts, low mood	0	1	2	3	4	5	6
Anxiety Feelings of stress; panic attacks	0	1	2	3	4	5	6

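### The SymptoMScreen proportion is labelled as moderate limitation or worse, but its cut-off of 4 is the severe category on the SAP's own 0-6 scale

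*SAP*

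**What the plan says.** SAP section 4.4.3.3 describes the SymptoMScreen as 12 items, each "scored on a 7-point likert scale", running from "0 = Not affect at all" to "6 = Total limitation/ I'm unable to do most daily activities". The middle codes are "3 = Moderate limitation/ I reduced my daily activities" and "4 = Severe limitation/ I gave up some activities". The total score has a stated range of 0-72 and is formed as follows: "The 12 items are summed for patients with all 12 questions non missing".

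The last sentence of the section adds a proportion at baseline and follow-up: patients with "at least one symptom causing moderate limitation (≥ 4) and above". It gives the follow-up visits as weeks 24, 46 and 96.

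The questionnaire in Protocol Appendix 5 prints the same coding, including "3 – moderate limitation/ I reduced my daily activities". Protocol section 4.5.9 mentions total and subscale scores but sets no threshold. SAP section 4 states that its analyses supersede those in the protocol, so this one sentence is the only specification of the proportion.

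**The concern.** The sentence gives the programmer a word and a number that disagree. The word takes in scores of 3 and above. The number takes in 4 and above, which on the printed scale begins at severe. Two competent programmers could produce different tables from it, and the one who follows the number would produce a result that does not match its label.

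What is at stake is how a reported percentage is read. A reader told that a given share of patients had a symptom of at least moderate limitation would in fact be seeing the share with at least severe limitation. Settling the cut-off after the data have been seen would also make it a post hoc choice.

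**Working it through.** **Inputs.** Item codes 0 to 6, 12 items, total range 0-72 and cut-off of 4 or more, all from SAP 4.4.3.3. Item codes on the patient form, from Protocol Appendix 5.

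**Step 1: which coding does the cut-off apply to?** The stated range settles it.
- Coding 0-6: minimum 12 × 0 = 0, maximum 12 × 6 = 72. This reproduces the stated 0-72.
- Coding 1-7: minimum 12 × 1 = 12, maximum 12 × 7 = 84. This does not.

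The second coding matters because it is the one under which 4 would mean moderate. It is ruled out.

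**Step 2: what does each cut-off select on the 0-6 coding?**

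| Cut-off | Levels counted | Number of levels |
|---|---|---|
| 4 or more | severe, very severe, total | 3 of 7 |
| 3 or more | moderate, severe, very severe, total | 4 of 7 |

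Only the second row matches the words of the label.

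**Step 3: who is missed?** Let M be a patient's highest item score at a visit. Then

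P(M ≥ 3) = P(M ≥ 4) + P(M = 3).

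The shortfall against the label is P(M = 3), the share of patients whose worst symptom is exactly moderate. It cannot be negative, and it is zero only if nobody has a worst score of 3. As an extreme case, a patient scoring 3 on every item has a total of 12 × 3 = 36 out of 72, yet is not counted at 4 or more. The same patient is counted at 3 or more.

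**Step 4: what happens to change from baseline?** Write q for P(M = 3). Then

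change at ≥ 4 = change at ≥ 3 − (q at follow-up − q at baseline).

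The sign of the bracket is unknown. With invented figures, suppose the proportion at 3 or more falls from 60% to 50% and the proportion at 4 or more falls from 35% to 30%. Then q goes from 60 − 35 = 25% to 50 − 30 = 20%, and the table at 4 or more shows a fall of 5 points instead of 10, a smaller improvement. If instead patients mainly move from a worst score of 4 to a worst score of 3, q rises and the table at 4 or more shows the larger improvement.

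**Step 5: the visit.** The mean-change summary in the same section, and the introduction to SAP 4.4.3, use weeks 24, 48 and 96. The schedules in Protocol Appendix 1 and SAP Appendix 2 place patient-reported outcomes at baseline and weeks 24, 48 and 96. There is no week 46 visit.

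**The case against.** The best defence is that very little depends on this sentence. The study is single-arm and descriptive, and the SymptoMScreen is exploratory. This proportion is an SAP addition with no test, sample size or decision rule attached. The total score and its mean change do not use the cut-off. SAP 4.4.3 also promises summaries of individual questions. All of that stands and keeps the point minor. It does not remove the contradiction, and separate item summaries cannot recover a worst-item proportion, which needs the items taken jointly within each patient.

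Could the number apply to something else? It cannot be a total-score threshold, because the sentence concerns at least one symptom. Nor does the form patients complete use another scale: its coding is the same, and its worked example links a score of 4 to giving an activity up completely.

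Some stronger readings are tempting but not supported:
- A reader might infer that every patient with moderate limitation is dropped. A patient with one symptom scored 3 and another scored 4 or more is still counted.
- A reader might infer that the cut-off makes the results over time look better. It applies at baseline too, so the direction is not known.
- A reader might infer that 3 was plainly intended. The documents do not show whether the word or the number is the slip.

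**Conclusion.** The inconsistency is real and nothing elsewhere in the documents resolves it. Followed as written, the sentence gives the proportion with severe or worse limitation under a label of moderate or worse. At any visit, the level is understated relative to that label by the share of patients whose worst symptom is scored exactly 3.

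That conclusion assumes the number is programmed literally. If the word is programmed instead, the table departs from the written cut-off. The documents give no distribution of item scores, so the shortfall cannot be sized, and any percentage-point figure would only restate an assumption. The effect on change from baseline is undetermined in both size and direction.

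This is a minor correction to one descriptive exploratory summary. The primary endpoint, the secondary endpoints and the main SymptoMScreen summaries are unaffected. The week 46 reference is a separate slip that adds no weight.

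**What to change.** Before analysis, adopt one of two wordings, which have equal standing because the documents do not reveal the intent:

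1. change the cut-off to 3 or more and keep the label as moderate limitation and above; or
2. keep the cut-off at 4 or more and relabel the outcome as severe limitation and above.

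In the same sentence, change week 46 to week 48.

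The cost is one line of SAP text. It needs no new data and no change to visits or procedures.

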4.4.3.4 Employment status: Work Productivity and Activity Impairment (WPAI)

The WPAI is a PRO formed of 6 items, used to assess working status, specifically the impact of MS on absenteeism, presentism, work productivity loss and activity impairment over the past 7 days.

Response options are:

Item #	Item Score	Details
1	Yes No	
2-4	Numerical	number of hours: 
 missed from work because of problems associated with MS missed from work because of any other reason; actually worked
5-6	numerical rating scale	Ranging from 0 to 10, where a higher score corresponds to MS problems highly impacting work/regular daily activities.

Four sub scores are calculated and presented as a percentage.

WPAI sub scores	Calculation for score (%)
Absenteeism (Percent work time missed due to problem)	$(Q2/(Q2+Q4)) * 100$
Presenteeism (Percent impairment while working due to problem)	$(Q5/10) * 100$
Work productivity (Percent overall work impairment due to problem)	$(Q2/(Q2+Q4)+[(1-(Q2/(Q2+Q4))x(Q5/10)]) * 100$
Activity Impairment (Percent activity impairment due to problem)	$(Q6/10) * 100$

Each WPAI sub score will be summarized descriptively by visit.

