7. How satisfied or dissatisfied are you with how easy the medication is to use?

- 1 Extremely Dissatisfied
- 2 Very Dissatisfied
- 3 Dissatisfied
- 4 Somewhat Satisfied
- 5 Satisfied
- 6 Very Satisfied
- 7 Extremely Satisfied

8. How satisfied or dissatisfied are you with how easy it is to plan when you will use the medication each time?

- 1 Extremely Dissatisfied
- 2 Very Dissatisfied
- 3 Dissatisfied
- 4 Somewhat Satisfied
- 5 Satisfied
- 6 Very Satisfied
- 7 Extremely Satisfied

Copyright © 2006 Quintiles Transnational Corp. All Rights Reserved.

9. How satisfied or dissatisfied are you by how often you are expected to use/take the medication?

- 1 Extremely Dissatisfied
- 2 Very Dissatisfied
- 3 Dissatisfied
- 4 Somewhat Satisfied
- 5 Satisfied
- 6 Very Satisfied
- 7 Extremely Satisfied

10. How satisfied are you that the good things about this medication outweigh the bad things?

- 1 Extremely Dissatisfied
- 2 Very Dissatisfied
- 3 Dissatisfied
- 4 Somewhat Satisfied
- 5 Satisfied
- 6 Very Satisfied
- 7 Extremely Satisfied

11. Taking all things into account, how satisfied or dissatisfied are you with this medication?

- 1 Extremely Dissatisfied
- 2 Very Dissatisfied
- 3 Dissatisfied
- 4 Somewhat Satisfied
- 5 Satisfied
- 6 Very Satisfied
- 7 Extremely Satisfied

Copyright © 2006 Quintiles Transnational Corp. All Rights Reserved.

Work Productivity and Activity Impairment Questionnaire:  
Specific Health Problem V2.0 (WPAI;SHP)

The following questions ask about the effect of your PROBLEM on your ability to work and perform regular activities. Please fill in the blanks or circle a number, as indicated.

1. Are you currently employed (working for pay)? \_\_\_\_\_ NO \_\_\_\_ YES  
If NO, check "NO" and skip to question 6.

The next questions are about the **past seven days**, not including today.

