2. During the past seven days, how many hours did you miss from work because of problems associated with your PROBLEM? Include hours you missed on sick days, times you went in late, left early, etc., because of your PROBLEM. Do not include time you missed to participate in this study.

\_\_\_\_\_ HOURS

3. During the past seven days, how many hours did you miss from work because of any other reason, such as vacation, holidays, time off to participate in this study?

\_\_\_\_\_ HOURS

[figure not shown]
4. During the past seven days, how many hours did you actually work?

\_\_\_\_\_ HOURS (If "0", skip to question 6.)

5. During the past seven days, how much did your PROBLEM affect your productivity while you were working?

*Think about days you were limited in the amount or kind of work you could do, days you accomplished less than you would like, or days you could not do your work as carefully as usual. If PROBLEM affected your work only a little, choose a low number. Choose a high number if PROBLEM affected your work a great deal.*

Consider only how much PROBLEM affected productivity while you were working.

[figure not shown]

CIRCLE A NUMBER

6. During the past seven days, how much did your PROBLEM affect your ability to do your regular daily activities, other than work at a job?

*By regular activities, we mean the usual activities you do, such as work around the house, shopping, childcare, exercising, studying, etc. Think about times you were limited in the amount or kind of activities you could do and times you accomplished less than you would like. If PROBLEM affected your activities only a little, choose a low number. Choose a high number if PROBLEM affected your activities a great deal.*

Consider only how much PROBLEM affected your ability to do your regular daily activities, other than work at a job.

CIRCLE A NUMBER

WPAUSer V2.0 (US English)

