4.7 MISSING DATA

All methods for handling missing data and associated sensitivity analyses are described above, section by section, for each endpoint. If not otherwise specified, missing values are not imputed.

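### WPAI overall work impairment is left missing, where it should be 100%, for employed patients who lost hours to MS and worked none, because the formula needs a question they are told to skip

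*SAP*

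**What the plan says.** SAP 4.4.3.4 defines four WPAI sub-scores: "Four sub scores are calculated and presented as a percentage". Absenteeism is Q2/(Q2+Q4), where Q2 is hours missed because of MS and Q4 is hours actually worked. Presenteeism is Q5/10. Overall work impairment combines the two as "Q2/(Q2+Q4)+[(1-(Q2/(Q2+Q4))x(Q5/10" (quoted without its closing brackets and the multiplication by 100). Q5 enters this expression with no condition attached.

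The WPAI form in Protocol Appendix 5 has two skip instructions. At Q1, patients who are not employed are told: "If NO, check 'NO' and skip to question 6". At Q4, patients who worked no hours are told: "If '0', skip to question 6". The second follows from the meaning of Q5, whose instruction reads "Consider only how much PROBLEM affected productivity while you were working".

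SAP 4.4.3.4 gives no rule for a skipped Q5. The general rule in SAP 4.7 is "If not otherwise specified, missing values are not imputed".

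**The concern.** Q5 is blank by design for every employed patient with Q4=0. A program that follows the SAP formula as written multiplies a zero weight by a missing value and returns missing.

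The patients removed in this way all have a true score of 100%, so the loss can only pull the visit mean down. The same patients stay in the absenteeism summary at 100%, so the two sub-scores describe different sets of patients. SAP 4.4.3 also plans summaries of change from baseline at Weeks 24, 48 and 96 for the exploratory endpoints. A patient with Q2>0 and Q4=0 at either time point would have no change in overall work impairment, and the effect on the mean change could go in either direction.

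The other questionnaires in the SAP do have rules for incomplete items: MSIS-29 (4.4.3.1), TSQM II (4.4.3.2) and SymptoMScreen (4.4.3.3). The TSQM II rule is the close parallel, because it gives a fixed value to items that an earlier answer made not applicable. The WPAI section has no counterpart.

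**Working it through.** **Inputs.** The formula and the 0 to 10 range of Q5 come from SAP 4.4.3.4, the skip at Q4=0 from Protocol Appendix 5, and the missing-data default from SAP 4.7. The plan states no figure for this score, so there is none to reproduce.

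**Notation.** Let A = Q2/(Q2+Q4) and P = Q5/10. The intended score is 100 × [A + (1−A) × P].

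**An ordinary record.** Q2=10, Q4=30, Q5=4: A = 10/40 = 0.25 and P = 0.4, so the score is 100 × (0.25 + 0.75 × 0.4) = 55%. The formula works when Q5 is present.

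**The affected record.** Q2=40, Q4=0, Q5 skipped: A = 40/40 = 1, so absenteeism is 100%. The weight on P is 1−A = 0.
- For any Q5 from 0 to 10, the score is 100 × (1 + 0 × P) = 100%.
- With Q5 missing, literal evaluation gives 1 + 0 × missing = missing.

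**Effect on a visit mean (illustration; both inputs assumed).** Let a share s of patients who should have a score be affected, and let the others average m. The mean with the affected patients at 100% is (1−s)m + 100s. The mean without them is m. The shortfall is s(100−m).

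| s | m | Mean with 100% included | Mean as computed | Shortfall (points) |
|---|---|---|---|---|
| 1% | 20% | 20.8% | 20% | 0.8 |
| 3% | 20% | 22.4% | 20% | 2.4 |
| 5% | 20% | 24.0% | 20% | 4.0 |
| 8% | 20% | 26.4% | 20% | 6.4 |
| 1% | 30% | 30.7% | 30% | 0.7 |
| 5% | 30% | 33.5% | 30% | 3.5 |

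**Brackets.** The full printed formula has six opening and five closing round brackets; the one before 1− is never closed. Closing it after Q2/(Q2+Q4) gives the intended form. Closing it after Q5/10 gives A + 1 − A × P, which is 100% for a patient with no lost hours and no impairment (Q2=0, Q4=40, Q5=0). That cannot be a percentage impairment, so only one reading is workable.

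**The case against.** The best case against the point is that it is small and that a sensible programmer would resolve it. WPAI is one of several exploratory endpoints in a single-arm, mainly descriptive study, and no test or primary, secondary or safety result depends on this sub-score. The SAP never says that the score is missing; that follows from one literal way of coding it. All of this stands and limits the weight of the point. It does not remove it, because the rule as written does not yield a value that the algebra fixes.

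A reader might infer more than the documents support:

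- **That SAP 4.7 forbids the correction.** It sets a default that gives way wherever something else is specified. Moreover, assigning 100% when Q5 has zero weight is algebra and needs no imputation.
- **That everyone affected lost the whole week to MS.** Q3 records hours missed for other reasons and is not in the formula. A patient with Q2=4, Q3=36, Q4=0 also has A = 4/4 = 1 and scores 100%, although most of the lost time was not due to MS. Patients who are not employed skip Q2 to Q5 by design and are untouched by this point.
- **That a change in the number off work would go unseen.** Absenteeism still records these patients at 100% at each visit, and the planned descriptive summaries include the number of patients, so differing denominators would show.
- **That the bracket would produce wrong scores.** The alternative reading is implausible on its face, and the lost bracket may come from reading the table out of the PDF.

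**Conclusion.** The point holds as a minor defect in a derivation. For employed patients with Q2>0 and Q4=0, the SAP taken literally gives a missing overall work impairment score where the correct value is 100%. This record-level result needs no assumption about Q5. It does rest on literal coding of the formula together with the no-imputation default.

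The visit mean is biased downward whenever such patients exist. The size is unknown, because the documents give neither the share affected nor the mean among the rest. The 0.8 to 6.4 percentage points for shares of 1% to 8% assume that the rest average 20%. The upper end needs a share that nothing in the documents supports, in a trial that enrols patients with a screening EDSS of 0.0 to 4.0. The primary NEDA analysis is unaffected.

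**What to change.** In SAP 4.4.3.4:

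1. State the score as 100 × [A + (1−A) × Q5/10], with A = Q2/(Q2+Q4). This also settles the bracket.
2. Add: if Q2>0 and Q4=0, overall work impairment is set to 100%; presenteeism stays missing.

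No further rule is needed for Q2=Q4=0. Absenteeism is then 0/0 and Q5 is skipped, so all three work scores are already undefined.

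The cost is two lines in the SAP and the matching lines in the derivation program. No new data are needed and no other endpoint changes.

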4.4.3.5 MRI and clinical outcomes at 6 months and 1 year

MRI data including total number of Gd-enhanced lesions up to Weeks 24 (*i.e. 6-months*) and 48 (*i.e. 1-year*), changes in total T2 lesion volume at Weeks 48 and changes in total T1 hypointense volume at Week 48 have been described as secondary efficacy endpoints.

Total number of new and/or enlarging T2 hyperintense lesions up to Weeks 24 and 48 will be summarized similarly to total number of T1 Gd-enhanced lesions (see section [4.4.2.10](#)).

4.4.3.6 Severity of relapses (hospitalization for MS relapse, use of corticosteroids, residual disability)

Severity of protocol defined relapses including hospitalization longer than 5 days (yes/no), use of corticosteroid (yes/no) and residual disability (yes/no) will be summarized at baseline, weeks 24, 48 and 96 using frequency tables (number and percentage with total number of relapses as denominator).

For protocol defined relapses, a descriptive analysis of the EDSS change between before and after relapse will be performed. This change in EDSS (referred as Chg-EDSS_(after-before)) will be defined as difference between EDSS collected at the last scheduled EDSS measurement available prior to relapse and the EDSS collected at the first scheduled or unscheduled EDSS measurement on or after relapse. Descriptive summary of Chg-EDSS_(after-before) will be presented along with the number of patients by EDSS change categories (≤ 0.5 , 0.5-1.0, 1.0-2.0 and >2.0).

To investigate the evolution of EDSS after relapse, the change between the first EDSS measurement after the relapse and the next scheduled EDSS measurement will be summarized as above. This will be repeated for the change between the first EDSS measurement after the relapse and the second next scheduled EDSS measurement.

To investigate the duration of post relapse residual disability, the number and proportion of patients with an $EDSS_{\text{after relapse} < 24; 48 > \text{weeks}} > EDSS_{\text{before relapse}} + 0.5 * \text{Chg-EDSS}_{(\text{after-before})}$ will be provided. This is illustrated in an example below:

$EDSS_{\text{before relapse}}$	$EDSS_{\text{after relapse}}$	$\text{Chg-EDSS}_{(\text{after-before})}$	$EDSS_{\text{after relapse} < 24 ; 48 > \text{weeks}}$	retained at least 50% of $\text{Chg-EDSS}_{(\text{after-before})}$
3	4	1	4.5	Yes
3	4	1	3.5	No

4.4.3.7 Proportion of patients who have NEDA, as per protocol defined events during a 96-week period and starting from baseline

This analysis can be considered as a sensitivity analysis of primary endpoint looking at clinical and MRI events in- between baseline visit and week 96. The MRI activity (T1 Gd-enhanced lesion and new/or enlarging T2 hyperintense lesion) will be evaluated from baseline to week 96.

Number and percentage of patients who have NEDA (yes, no) according to the presence of T1 Gd-enhanced lesion at Week 8 will be provided.

This endpoint will be analyzed similarly to the primary endpoint as described in section [4.4.1](#).

4.4.3.8 Predictors of NEDA and association between NEDA and disability or other efficacy parameters

Logistic regression models will be used to identify predictors of response to treatment (freedom from events). Variables that will be considered include:

- Duration since MS Symptom Onset (≤ 3 years, >3 and ≤ 5 years, >5 years and ≤ 10 years, >10 years),
- T2 volume at week 8 (since not available at screening),
- presence of T1 Gd-enhanced lesions at screening,
- presence of relapses prior screening as per CRF (Yes/No)
- number of previous DMTs (1, >1)
- baseline EDSS
- gender.

4.4.3.9 Epoch analysis of NEDA in Year 1 (Weeks 0 to Week 48) and Year 2 (Week 48-96)

This analysis will be performed on the mITT population. Note, this is an additional endpoint as compared with the protocol.

The analysis of NEDA in Year 1 will follow the same rule as in Section 4.4.2.1. For the definition of EDA events in Year 2, a new baseline at week 48 for CDP and MRI activity

will be considered. A cross tabulation table of patients with NEDA = Yes/No in Year 1 and Y2 will be also presented.

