### **2.1.3 Exploratory Efficacy Objective**

The exploratory efficacy objective for this study is to further assess the efficacy of ocrelizumab 600 mg IV given every 24 weeks by monitoring patient-reported outcomes (PROs) related to quality of life (QoL), treatment satisfaction and other endpoints or analyses as follows:

- Multiple Sclerosis Impact Scale (MSIS)-29 (MS-specific QoL questionnaire)
- Treatment satisfaction questionnaire for medication (TSQM II)
- Patient reported outcome: SymptoMScreen
- MRI and clinical outcomes at 6 months and 1 year
- Predictors of NEDA and association between NEDA and disability or other efficacy parameters
- Severity of relapses (hospitalization for MS relapse, use of corticosteroids, residual disability)
- Employment status (WPAl)
- Proportion of patients who have NEDA, as per protocol defined events during a 96-week period and starting from baseline

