### **5.3.5.11 Hospitalization or Prolonged Hospitalization**

Any adverse event that results in hospitalization (i.e., in-patient admission to a hospital) or prolonged hospitalization should be documented and reported as a serious adverse event (per the definition of serious adverse event in Section 5.2.2), except as outlined below.

The following hospitalization scenarios are not considered to be adverse events:

- Hospitalization for respite care
- Hospitalization for a preexisting condition, provided that all of the following criteria are met:
  - The hospitalization was planned prior to the study or was scheduled during the study when elective surgery became necessary because of the expected normal progression of the disease
  - The patient has not experienced an adverse event

The following hospitalization scenarios are not considered to be serious adverse events, but should be reported as adverse events instead:

- Hospitalization that was necessary because of patient requirement for outpatient care outside of normal outpatient clinic operating hours.
- Elective hospitalizations or surgical procedures that are a result of a patient's pre-existing condition(s) that have not worsened since receiving trial medication. Examples may include, but are not limited to, cholecystectomy for gallstones, and diagnostic testing. Such events should still be recorded as medical procedures in the "Surgeries and therapies" eCRF.
- Hospitalization to receive trial medication such as infusions of ocrelizumab unless this is prolonged (more than 24 hours).
- Hospitalization following an MS relapse as long as the reason for hospitalization is to receive standard treatment with i.v. methylprednisolone.

For a list of serious ADRs that are considered expected, kindly refer to the current IB.

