4. STATISTICAL METHODS

For continuous variables, descriptive statistics (e.g., number of patients [n], mean, standard deviation [SD], median, 25th and 75th percentiles, minimum, maximum) will be calculated and summarized.

For categorical variables, the number and percentage in each category will be displayed.

Statistical methods for analysis of efficacy variables are detailed in the Efficacy Analyses section below.

Unless otherwise specified, statistical tests will be two-sided and the statistical significance level will be 5%. Corresponding 95% CIs will be presented as appropriate. Although multiple statistical tests may be conducted, no adjustments to the Type 1 error rate will be made.

The analyses outlined in this SAP supersede those specified in the protocol.

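### The relapse-severity endpoint is hospitalisation for relapse of any length, but the SAP tabulates only stays longer than 5 days, so admissions of 1 to 5 days cannot be told apart from no admission

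*SAP*

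**What the plan says.** Protocol 2.1.3 lists the exploratory item as "Severity of relapses (hospitalization for MS relapse, use of corticosteroids, residual disability". The protocol synopsis, SAP 2.2.3 and the heading of SAP 4.4.3.6 use the same wording. None of these four places sets a minimum stay.

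The first sentence under the SAP 4.4.3.6 heading defines what will be tabulated: "Severity of protocol defined relapses including hospitalization longer than 5 days (yes/no". Corticosteroid use and residual disability follow as the other yes/no items. All are to be summarised "using frequency tables (number and percentage with total number of relapses as denominator". No row for admission of any length is specified, and no category for 1 to 5 days.

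SAP section 4 states: "The analyses outlined in this SAP supersede those specified in the protocol". The longer-than-5-days variable is therefore the one that would be run.

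**The concern.** The stated item and the planned variable are different quantities. The first counts every relapse that led to admission; the second counts only those with a stay beyond 5 days. Under the plan as written, the stated item is not reported anywhere.

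This is a single-arm study with no comparator, so the absolute percentage is itself the result. A reader who takes the figure as the share of relapses hospitalised, as the section heading invites, would have a number that is too low whenever any admission was short.

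The cut is also undeclared. The SAP comments on other departures from the protocol: it explains why time to first new or enlarging T2 lesion is not analysed (4.4.2.8), and it marks the grey matter, white matter and epoch analyses as additions (4.4.2.15, 4.4.2.16, 4.4.3.9). It says nothing comparable about the 5-day threshold.

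**Working it through.** There is no planned figure to reproduce. The check is a comparison of texts plus a short identity.

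**Texts side by side**

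| Place | Hospitalisation item | Length of stay |
|---|---|---|
| Protocol synopsis, exploratory objectives | for MS relapse | none |
| Protocol 2.1.3 | for MS relapse | none |
| SAP 2.2.3 | for MS relapse | none |
| SAP 4.4.3.6, heading | for MS relapse | none |
| SAP 4.4.3.6, analysis text | yes/no | more than 5 days |

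The precedence rule in SAP section 4 settles protocol against SAP. It does not settle SAP 4.4.3.6 against SAP 2.2.3 or against its own heading, because all three are in the SAP.

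**What the table would show.** Let N be the number of protocol-defined relapses, A the number with any admission, and L the number with a stay over 5 days, so that L ≤ A ≤ N.

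- Stated item: h = A/N.
- Share of admissions lasting 5 days or fewer: s = (A − L)/A.
- Planned item: L/N = h(1 − s).
- Planned no cell: N − L = (N − A) + (A − L). The first term is relapses never admitted; the second is relapses admitted for 1 to 5 days. The table gives only their sum.

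Since s lies between 0 and 1, the planned percentage lies between 0 and h. It equals h only if every admission exceeded 5 days.

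**Size.** The documents give neither h nor s. Taking s as an assumption, the fraction of hospitalised relapses still visible is 1 − s:

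- s = 25%: 1 − 0.25 = 75%
- s = 50%: 1 − 0.50 = 50%
- s = 75%: 1 − 0.75 = 25%

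These fractions do not depend on h. They illustrate the formula and are not estimates for this trial.

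**Whether another planned output recovers the short stays.** Protocol 5.3.5.10 says relapses are not to be recorded as adverse events and are captured as efficacy data only. Protocol 5.3.5.11 lists, among admissions that are not serious adverse events, "Hospitalization following an MS relapse as long as the reason for hospitalization is to receive standard treatment with i.v. methylprednisolone". SAP 4.6.2 includes serious relapses among its serious events, but admissions under that exemption would not be among them. The same protocol section says such admissions should be reported as adverse events instead, which sits awkwardly with 5.3.5.10, so capture there may be incomplete. The corticosteroid item in SAP 4.4.3.6 does not separate inpatient from outpatient treatment.

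**The case against.** The strongest reply is that the protocol names three severity domains without defining variables, leaves full analysis details to the SAP (protocol section 6), and is superseded by it. A duration threshold is one reasonable way to grade severity, and the word including leaves room for further summaries. Part of this stands: the SAP may choose a threshold. But it should say so and why, and its outcome list and heading should match. As written, no further summary is listed.

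A reader might also infer more than the documents support:

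- *That short admissions are reported as not hospitalised.* The variable is explicitly named as a stay longer than 5 days, so a no answers that question only. The defect is loss of distinction, not a false label.
- *That the relapses lost are the ones admitted for steroids.* Protocol 5.3.5.11 gives no length of stay for such admissions, and no other section does. It might even suggest a motive for the threshold, since the protocol already treats them as less serious, but the SAP does not state that motive.
- *That relapse severity as a whole will look milder than it was.* SAP 4.4.3.6 also reports corticosteroid use, residual disability, EDSS change around the relapse and retained disability. Severity does not rest on this item alone, and in a single-arm study no between-arm comparison is biased.
- *That the adverse event page can supply the missing admissions.* The two protocol sections above make that unreliable. SAP 4.6.2 names a combined adverse event, infusion reaction and relapse form, but the documents do not show whether it records admissions of any length.

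**Conclusion.** The mismatch is real and minor. As planned, the hospitalisation row reports h(1 − s) where the stated item is h. The direction is certain: at or below the stated item. The size is unknown, because neither quantity is in the documents. The conclusion rests on the SAP text being executed as written, with no any-duration row added at the programming stage.

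The item is exploratory and descriptive. NEDA, the annualised relapse rate, confirmed disability progression and the sample size are not touched.

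**What to change.** In SAP 4.4.3.6, tabulate hospitalisation for MS relapse of any duration (yes/no) as the stated item, and keep the longer-than-5-days item as an additional row with the same denominator. The cost is about one sentence and one table row, provided the relapse eCRF records any admission.

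If that eCRF holds only the longer-than-5-days field, the stated item cannot be produced from it. In that case label the row and any conclusion as stays longer than 5 days, declare the departure from the protocol with its reason, and bring SAP 2.2.3 and the section heading into line. Do not fill the gap from adverse event or serious adverse event records, where capture of relapse admissions may be incomplete.
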